## 7.1 RECRUITMENT PLAN

Potential research subjects will be identified by a member of the patient's treatment team, the protocol investigator or research team within the Gynecologic Medical Oncology Group at Memorial Sloan-Kettering Cancer Center (MSKCC). Patient recruitment will occur in the Gynecologic Medical Oncology clinics at MSKCC. The investigator will discuss the study with suitable participants, and should the patient consent to proceed with protocol therapy, will enroll their patient's in the research study. Based on historical accrual rates in similar populations, we anticipated successful enrollment of 2 patients per month yielding a total accrual time of 12 months. However, due to a slower than expected accrual rate, we have expanded the eligibility to allow patients who have received up to 4 prior lines of therapy to be eligible. We believe that with this modification, we will be able to accrue approximately 2 patients per month onto this study.

Patients must have PI3K pathway activation defined as EITHER of the following:

1. Genomic alteration resulting in loss of PTEN function including a) whole or partial gene deletion, frame shift mutations, or non-sense mutations. Missense mutations in PTEN will not be considered qualifying.
2. A previously characterized activating mutation in any component of the pathway including: PIK3CA, AKT1, PIK3R1, PIK3R2, mTOR

Patients must also not have a known concurrent activating RAS/RAF mutation or loss of function alteration in NF1 or NF2 resulting in MAP kinase pathway activation.

Any mutational profiling performed in a CLIA laboratory either as routine standard of care or as part of a dedicated genomic profiling study such as MSKCC IRB# 12-245 will be accepted. For patients who have not had mutational profiling performed in a CLIA laboratory or as part of a prior genomic profiling study, formally consenting to MSKCC IRB# 12-245 Part A will be required before consenting to the current study to ensure that the consenting patient has a PI3K pathway activating mutation as detailed above.

Patients who respond to therapy and then progress will be offered a consent to MSKCC IRB# 12-245 Part B in order to obtain post-progression material for molecular profiling in order to determine the mechanism(s) underlying acquired resistance. Participation in this companion study is optional for enrolled patients. IRB# 12-245 Part B is a separate consent, but it is similar to IRB# 12-245 Part A. IRB# 12-245 Part B consent is specifically utilized in cases where patients have received experimental targeted therapy and are undergoing repeat mutation profiling of post-treatment malignancy in an effort to determine the mechanism(s) underlying acquired resistance. Specifically, we will be looking for presence of genetic alterations which based on their understood biological mechanism may explain acquired resistance (for example, second “hits” on the PI3K pathway).

## **8.1 PRETREATMENT EVALUATION**

### **Within 28 days prior to treatment start:**

- History and Physical examination
- Review of concomitant medications
- Vital signs (blood pressure, heart rate and temperature), weight and height
- Performance status
- Toxicity assessment
- 12-lead ECG
- Radiographic tumor measurements (CT C/A/P, MRI, Chest X-ray)
- Hepatitis B and C screening
- Request archival tumor tissue (if required and done through IRB 12-245)

### **Within 7 days prior to treatment start:**

- Complete Blood Count (CBC) with differential and platelets

- Comprehensive profile (BUN, creatinine (or creatinine clearance), sodium, potassium, chloride, CO2, calcium, total bilirubin, total protein, albumin, alkaline phosphatase, AST, ALT)
- Phosphorus
- Magnesium
- PT/PTT
- CA125
- Hemoglobin A1c
- Insulin Level
- Fasting blood glucose
- Body weight
- Urinalysis
- Pregnancy test (in women of child bearing potential)

## **9.1 TREATMENT/INTERVENTION PLAN**

### **9.2 Treatment**

LY3023414 200 mg will be dosed orally twice a day. Each cycle will be 21 days in duration. Patients will receive study treatment until disease progression, intolerable toxicity, elective withdrawal from the study, study completion, or study termination. In limited circumstances patients may be treated beyond progression if, in the opinion of the Principal Investigator, the patient is benefiting from treatment. Approval from Eli Lilly will be required in these circumstances.

LY3023414 should be taken approximately 12 hours apart. Patients should not consume food for approximately 1 hour before taking the dose of LY3023414. If a dose is vomited within one hour of ingestion, it will be replaced. If vomiting occurs more than 1 hour after dosing, it will be considered a complete dose and will not be replaced.

### **Concomitant medication and treatment**

Concomitant medication is defined as any prescription or over-the-counter preparation, including vitamins and supplements. Patients may continue their baseline medication(s). All concomitant medication(s) must be recorded. Any diagnostic, therapeutic or surgical procedure performed during the study period should be recorded, including dates, description of the procedure(s) and any clinical findings.

LY3023414 is a weak inhibitor of cytochrome P450 3A4 (CYP3A4) in patients and thereby impacts (decreases) the metabolic clearance of drugs that are metabolized through CYP3A4 (See also IB Section 6.1.2). The clinical implications of this risk have yet to be determined. Patients should avoid taking concomitant medications that are CYP3A4 substrates (for example, midazolam).

Investigators should monitor patients for unexpected clinical adverse effects as a result of unexpected high exposure to LY3023414 due to any potential interaction of concomitant medications with LY3023414.

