Initial clinical LY3023414 pharmacokinetic/pharmacodynamic (PK/PD) data showed that LY3023414 maximum plasma concentration ( $C_{max}$ ) and area under the plasma concentration-time curve ( $AUC_{\infty}$ ) increased approximately dose-proportionally from 20 to 325 mg QD (that is within the QD dose range determined to be safe). However, the  $C_{max}$  and  $AUC_{\infty}$  increase was greater than dose proportional at 450 mg QD (i.e., that is at the dose exceeding the MTD). LY3023414 PK data following repeated BID dosing (dose range of 150 to 250 mg BID) were consistent with PK data following 20 to 325 mg QD. The oral clearance (CL/F) ranged from approximately 77 to 130 L/hour across the 20 to 325 mg dose range associated with an oral volume of distribution (V/F) ranging from 185 to 315 L in that same dose range. This clearance and volume lead to mean half-life ( $t_{1/2}$ ) of 2.07 hours (coefficient of variation [CV] = 45%, n = 35), consistent with the prediction.

The relative contribution of microsomal CYP-mediated clearance of LY3023414 was studied in vitro using human liver microsomes. Based on a substrate depletion approach, CYP 3A4 and CYP1A2 are responsible for 82% and 18% of hepatic CYP-mediated clearance of LY3023414, respectively. No in-vivo data are yet available.

The recent data from study CBBA indicate that LY3023414 is a weak inhibitor of CYP3A4. Concomitant administration of LY3023414 and midazolam lead to increase in midazolam exposure (fold increase: mean 1.459 [CV 30.5 %] [90% CI 1.21 – 1.76]). Hence LY3023414 may lead to increase in exposure of CYP3A4 substrate. Considering that CYP2C8, not CYP3A4, is the most relevant and major enzyme responsible for enzalutamide clearance and that the inhibitory effect of LY3023414 on CYP3A4 is weak, it is not anticipated that enzalutamide exposure will be significantly increased (i.e. > 1.5 fold change) after coadministration with LY3023414.

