16. Known untreated or active central nervous system (CNS) metastases (progressing or requiring anticonvulsants or corticosteroids for symptomatic control). Patients with a history of treated CNS metastases are eligible, provided that they meet all of the following criteria:
  - a. Presence of measurable disease outside the CNS
  - b. No radiographic evidence of worsening upon the completion of CNS-directed therapy and no evidence of interim progression between the completion of CNS-directed therapy and the screening radiographic study
  - c. No history of intracranial hemorrhage or spinal cord hemorrhage
  - d. No ongoing requirement for dexamethasone as therapy for CNS disease (anticonvulsants at a stable dose are allowed)
  - e. Absence of leptomeningeal disease
17. Inability to comply with study and follow-up procedures.
18. Any other disease, metabolic dysfunction, physical examination finding, or clinical laboratory finding that, in the investigator's opinion, gives reasonable suspicion of a disease or condition that contraindicates the use of an investigational drug or that may affect the interpretation of the results or render the patient at high risk from treatment complications.

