## 11.1 TOXICITIES/SIDE EFFECTS

The dose delay and reduction instructions provided in Tables 11A and 11B are intended to serve as guidelines to allow ongoing treatment for patients experiencing clinical benefit without signs or symptoms of progression while ensuring patient safety. Patients may temporarily suspend dosing of LY3023414 for up to 14 days if they experience toxicity that is considered related to LY3023414 and requires that a dose be held. Patients who miss ≥ 14 consecutive days of scheduled LY3023414 treatment because of LY3023414 related AEs will be discontinued from the study. LY3023414 dosing delay beyond 2 weeks and up to 28 days may be permissible, if AEs are not considered to be primarily related to LY3023414 and the investigator deems continuation to have clinical benefit for the patient. Exceptions may be made after discussion with the approval by the Principal Investigator. Patients may suspend dosing of study drug for radiation therapy or surgery that is considered by the treating physicians to be of clinical benefit for the patient. After completion of the intervention, patients may restart the study drug as long as all criteria for dosing are met and there is no evidence of disease progression (unless approved by PI and sponsor as noted previously).

Dose modifications for LY3023414 for select AEs, should follow the guidance provided in Table 11A, and required dose reductions should follow the dose levels outlined in Table 11B. No dose re-escalation will be allowed.

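### Section 9 lets baseline medications continue with no limit on strong CYP3A4 inhibitors or inducers, although CYP3A4 is the study drug's main hepatic CYP route in vitro and the dose is the twice-daily MTD

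*Combined protocol and SAP*

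**What the plan says.** Concomitant medication and treatment (Section 9) counts prescription drugs, over-the-counter products and supplements as concomitant medication, and requires all of it to be recorded. It opens with a general permission: "Patients may continue their baseline medication(s)". It then describes LY3023414 as a weak CYP3A4 inhibitor and restricts one class: "Patients should avoid taking concomitant medications that are CYP3A4 substrates (for example, midazolam)". For interactions in the other direction it gives one instruction: "Investigators should monitor patients for unexpected clinical adverse effects as a result of unexpected high exposure to LY3023414".

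Ongoing Studies and Clinical Safety (Section 3) reports from human liver microsomes that "CYP 3A4 and CYP1A2 are responsible for 82% and 18% of hepatic CYP-mediated clearance of LY3023414, respectively", and adds that in vivo data are not yet available. The same section sets 200 mg as the MTD for twice-daily dosing, which is the dose used here.

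Exclusion criterion 16 deals with brain metastases: "Patients with a history of treated CNS metastases are eligible, provided that they meet all of the following criteria". Under item d, "anticonvulsants at a stable dose are allowed", with no reference to enzyme induction. Section 8.1 already lists "Review of concomitant medications" within 28 days before treatment. On dose reductions, Section 11.1 says "No dose re-escalation will be allowed".

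No limit on strong CYP3A4 inhibitors or inducers appears in the eligibility criteria (6.1, 6.2), the dosing text (4.2, 5.0, 9.2), the dose-modification rules (11.1, Tables 11A and 11B) or the removal criteria (13.1).

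**The concern.** The restriction covers what LY3023414 does to other drugs, where the measured effect is weak (midazolam exposure up 1.459-fold on average). Nothing restricts what other drugs may do to LY3023414, where the protocol's own in vitro data name CYP3A4 as the leading CYP route. The monitoring sentence shows that raised exposure from an interaction was foreseen, but it asks for detection only.

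Two things are at stake. A patient who enters on a strong inhibitor would start at the MTD with exposure raised by an unknown amount. A patient who enters on a strong inducer may be under-dosed, and monitoring for adverse effects cannot reveal that. If toxicity leads to a dose reduction, the bar on re-escalation keeps the lower dose in place even after the interacting drug is stopped.

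**Working it through.** **Design figures.** With 25 patients and success at 5 or more responses, the exact binomial gives P(X ≥ 5 | 0.10) = 0.098 and P(X ≥ 5 | 0.30) = 0.910. These agree with the stated 10% type I error and 90% power.

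**Margin above the dose.** The next twice-daily level tested was 250 mg, and 250/200 = 1.25. Reading this as 1.25-fold exposure relies on Section 3, which reports roughly dose-proportional exposure from 20 to 325 mg once daily and consistent data for 150 to 250 mg twice daily.

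**DLTs at the two levels (Section 3).** 3 of 4 at 250 mg (Clopper-Pearson 95% CI 19% to 99%) against 1 of 6 at 200 mg (0.4% to 64%); Fisher two-sided p = 0.19. This contrast is weak.

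**Break-even for an inhibitor.** Let f be the hepatic CYP share of total clearance (not given) and i the fraction of CYP3A4 inhibited. Then

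fold = 1 / (1 − 0.82 × f × i).

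A 1.25-fold rise needs 0.82 × f × i = 1 − 1/1.25 = 0.20, so f × i = 0.20/0.82 = 0.244. With complete block (i = 1), f must be at least 24.4%; below that, CYP3A4 inhibition cannot reach the 250 mg level.

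**Range under assumed f.** The induction column uses fold = 1 / (1 + 0.82 × f × (E − 1)), with an assumed fivefold rise in CYP3A4 activity (E = 5).

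| f | complete block | 80% inhibition | fivefold induction |
|---|---|---|---|
| 25% | 1.26 | 1.20 | 0.55 |
| 50% | 1.69 | 1.49 | 0.38 |
| 75% | 2.60 | 1.97 | 0.29 |
| 100% | 5.56 | 2.91 | 0.23 |

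The only pointer to f is in Nonclinical Pharmacokinetics/Pharmacodynamics, where preliminary rat data suggest mainly oxidative clearance. That favours f above 24% only if humans resemble rats and the oxidation is by CYP. The same text also reports conjugative metabolites in rat and dog plasma.

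**Effect on the response test.** Suppose 1 of 25 patients takes an inducer and has a 10% rather than 30% chance of response (assumption). Power is then 0.9 × P(X ≥ 5 of 24 | 0.30) + 0.1 × P(X ≥ 4 of 24 | 0.30) = 0.9 × 0.8889 + 0.1 × 0.9576 = 0.896, down from 0.910. Type I error at a 10% response rate stays at 0.098.

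**The case against.** The best reply is that the plan already contains the risk.

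- **Entry criteria.** Active infection needing antibiotics (uncomplicated urinary infection excepted), known HIV, active hepatitis B or C, chronic steroids at 10 mg or more of prednisone equivalent, and dexamethasone for CNS disease are all barred. These may remove some sources of interacting drugs at entry. That stands as a narrowing, but none of them names the drug classes at issue or covers drugs started later.
- **Substrate sentence.** Some strong inhibitors or inducers may themselves be CYP3A4 substrates and so fall under it. The documents do not say which, and the overlap would not be complete.
- **Dose rules.** A reader might infer that Table 11A would send a patient with interaction-driven toxicity back to the same dose. The documents do not support that for the harms seen at 250 mg. Those DLTs were hypophosphatemia, fatigue and mucositis, which have no row of their own. They fall under the row for other drug-related events, where Grade 3-4 means hold and restart one level lower. Same-dose restart is directed for short-lived Grade 2 hyperkalemia and a first Grade 3 rash. The first reduction, 200 to 150 mg, offsets a 200/150 = 1.33-fold rise, which is more than 1.25. This objection stands, and with the Day 8 and Day 15 visits it is real mitigation. It still acts only after toxicity.
- **Early tolerability.** Among 31 patients at or below the two MTDs there were no drug-related Grade 4 events and six possibly related Grade 3 events. This is reassuring about the dose itself. It does not speak to the dose taken with a strong inhibitor.
- **Investigator's Brochure.** It may hold guidance and cannot be seen here. Section 9 cites it only for the effect on CYP3A4 substrates, while expressly allowing baseline drugs. A small part of the Section 3 background was also not available for this check.

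**Conclusion.** The gap holds and should be closed, with medium confidence. A stated permission, read with the protocol's own clearance data and a starting dose at the MTD, allows an avoidable exposure risk in one direction and leaves under-exposure unaddressed in the other.

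The size of the harm is not established. It depends on f, which the documents do not give, and on how many patients take such drugs, which they do not give either. Below f of about 24% even complete block stays under the 250 mg equivalent; above it, the exposure could be well beyond.

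Two stronger inferences are not supported. One is that patients on strong inhibitors would in fact reach the exposure at which 3 of 4 had DLTs: neither f nor the DLT contrast is firm enough for that. The other is that the response test is compromised: under the single-inducer assumption power moves by 1.4 points (0.910 to 0.896), and the sample size, cut-off and type I error do not change. This is a point of patient safety and tolerability.

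**What to change.** Replace the permission in Section 9 with: *Patients may continue baseline medications except strong CYP3A4 inhibitors and strong CYP3A4 inducers, which should be stopped or substituted before the first dose and avoided on treatment; a patient who cannot stop or substitute should not be enrolled.*

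Apply the same exception to the anticonvulsants in exclusion criterion 16d, which concerns only patients with treated CNS metastases. Clinical pharmacology should take the drug list, and any washout, from the Investigator's Brochure. Check compliance at entry through the medication review in Section 8.1. The Section 10 schedule has no row for concomitant medication on treatment, so from then on use the recording that Section 9 already requires, at the existing visits. Keep the substrate sentence, and leave weaker inhibitors under the present monitoring sentence.

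The cost is two wording changes and a drug list, with no new visit, test or analysis. An occasional patient will need a drug switch. Rarely, one will be ineligible, in a trial whose recruitment plan (Section 7.1) already reports slow accrual.

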### 9.3 Correlative Studies

Cell Free DNA: 2 extra Streck BCT tubes will be collected at the time of routine blood collection at the specified time points in the calendar in Section 10.0. Processing will occur per MSKCC laboratory medicine procedures.

## 10.0 EVALUATION DURING TREATMENT/INTERVENTION

PARAMETER	Screening		Cycle 1			Cycle 2+	End of Treatment	Follow-up
Day	28 days before start	7 Days before start	1	8 ±3 days	15 ±3 days	1 ±4 days	30 days ±14 days	Every 3 months until death ±1 month
Medical History	X							
Physician Examination	X		X	X	X	X	X	
Performance Status	X		X	X	X	X	X	
Height	X							
Weight		X	X	X	X	X	X	
Vital Signs (blood pressure, heart rate and temperature)	X		X	X	X	X	X	
Adverse Event Assessment			X	X	X	X	X	
CBC, differential, hemoglobin, platelets, Electrolytes, BUN, Creatinine, Ca, Mg, Phosphorus, Bilirubin, AST/SGOT, ALT/SGPT, Alkaline Phosphatase		X	X 	X	X	X	X	
Fasting (≥8 hours) Blood Glucose		X	X 	X	X	X	X	
Insulin Level		X	X 	X	X	X	X	
Hemoglobin A1c		X	X 			X	X	

PARAMETER	Screening		Cycle 1			Cycle 2+	End of Treatment	Follow-up
Day	28 days before start	7 Days before start	1	8 ±3 days	15 ±3 days	1 ±4 days	30 days ±14 days	Every 3 months until death ±1 month
PT, INR, PTT		X					X	
Pregnancy test		X 					X	
CA125		X	X 			X	X	
Electrocardiogram	X			X		X	X	
CELL-Free DNA			X	X		X (Odd cycles Day 1 only)		
Radiographic disease assessment	X					X 	X 	X 
Patient drug diary					X			
Survival Follow-up								X 

1. If the patient is of child-bearing potential per MSKCC guidelines. Must be obtained within 72 hours prior to initiating protocoltherapy.
2. Study can be omitted on Cycle 1 Day 1 with screen labs performed within 72 hours.
3. Performed during week 3 of each even numbered cycle (Days 15-21).
4. Only if patient discontinues for reasons other than progression, repeated every 3 months +/- 2 weeks until disease progression or initiation of alternative anti-cancer therapy.
5. Phone call every 3 months.

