### **13.1 CRITERIA FOR REMOVAL FROM STUDY**

Patients may withdraw from the study at any time. Any patient who withdraws will be encouraged to return to the study center for a treatment completion visit. Patients who

discontinue early should return within 30 days following the final dose of study treatment. The primary reason for discontinuation must be recorded in the medical record.

Patients may be withdrawn from the study if they experience any of the following:

- Disease progression, per investigator assessment
- Intolerable toxicity of LY3023414

Other reasons for patient discontinuation may include, but are not limited to, the following:

- Change in patient eligibility
- Non-compliance
- Patient decision
- If the patient becomes pregnant
- If patient requires more than 2 dose reductions of LY3023414
- If treatment is delayed for more than 28 consecutive days

The investigator has the right to discontinue a patient from the study for any medical condition that the investigator determines may jeopardize the patient's safety if he or she continues in the study; for reasons of noncompliance (e.g., missed doses, visits); or if the investigator determines it is in the best interest of the patient.

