### **17.2 Serious Adverse Event(SAE) Reporting**

An adverse event is considered serious if it results in ANY of the following outcomes:

- Death
- A life-threatening adverse event
- An adverse event that results in inpatient hospitalization or prolongation of existing hospitalization
- A persistent or significant incapacity or substantial disruption of the ability to conduct normal life functions
- A congenital anomaly/birth defect
- Important Medical Events (IME) that may not result in death, be life threatening, or require hospitalization may be considered serious when, based upon medical judgment, they may jeopardize the patient or subject and may require medical or surgical intervention to prevent one of the outcomes listed in this definition

Note: Hospital admission for a planned procedure/disease treatment is not considered an SAE.

SAE reporting is required as soon as the participant signs consent. SAE reporting is required for 30-days after the participant's last investigational treatment or intervention. Any events that occur after the 30-day period and that are at least possibly related to protocol treatment must be reported.

If an SAE requires submission to the IRB office per IRB SOP RR-408 'Reporting of Serious Adverse Events', the SAE report must be sent to the IRB within 5 calendar days of the event. The IRB requires a Clinical Research Database (CRDB) SAE report be submitted electronically to the SAE Office as follows:

For IND/IDE trials: Reports that include a Grade 5 SAE should be sent to [[contact]](mailto:[contact]). All other reports should be sent to [[contact]](mailto:[contact]).

For all other trials: Reports that include a Grade 5 SAE should be sent to [[contact]](mailto:[contact]). All other reports should be sent to [[contact]](mailto:[contact]).

The report should contain the following information:

Fields populated from CRDB:

- Subject's initials
- Medical record number
- Disease/histology (if applicable)
- Protocol number and title

Data needing to be entered:

- The date the adverse event occurred
- The adverse event
- The grade of the event
- Relationship of the adverse event to the treatment (drug, device, or intervention)
- If the AE was expected
- The severity of the AE
- The intervention
- Detailed text that includes the following
  - A explanation of how the AE was handled
  - A description of the subject's condition
  - Indication if the subject remains on the study

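### The calendar allows the last adverse event assessment before day 30 after the last dose, so up to 14 days of the 30-day SAE window can pass with no scheduled AE contact

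*Combined protocol and SAP*

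**What the plan says.** **Calendar (Section 10.0).** The End of Treatment column is headed "30 days ±14 days". The row "Adverse Event Assessment" is marked on Cycle 1 days 1, 8 and 15, on day 1 of each later cycle, and at End of Treatment. It is blank in the Follow-up column, which is headed "Every 3 months until death ±1 month". That column holds two entries: imaging for patients who stopped for reasons other than progression (footnote 4), and survival follow-up, which footnote 5 describes as "Phone call every 3 months".

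**SAE reporting (Section 17.2).** "SAE reporting is required for 30-days after the participant's last investigational treatment or intervention". The section then adds: "Any events that occur after the 30-day period and that are at least possibly related to protocol treatment must be reported". Section 17.2.1, meant for further SAE instructions, contains only placeholder text.

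**Removal from study (Section 13.1).** Patients who "discontinue early should return within 30 days following the final dose of study treatment". No earliest day is given.

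**Toxicity (Section 11.1).** Patients who miss 14 or more "consecutive days of scheduled LY3023414 treatment because of LY3023414 related AEs will be discontinued from the study", with exceptions possible on the Principal Investigator's approval.

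**Use of the data.** Safety and tolerability is secondary objective 5 (Section 2.2). It is analysed as a tabulation of adverse events (Section 14.1, item 5).

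**The concern.** The protocol sets a 30-day post-treatment period for SAEs but lets its last scheduled look for adverse events happen about halfway through it. After an early visit, nobody is scheduled to ask the patient about adverse events again. SAEs in the remaining days would then come to light through spontaneous report or routine care. Non-serious events after the visit have no stated collection route at all.

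A second gap has the same cause. No section provides for following an adverse event to resolution or stabilisation once treatment ends. A patient taken off study for drug-related toxicity may still have it at End of Treatment, and the schedule would not record whether it cleared.

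What is at stake is the completeness of the safety tabulation, including its ability to show reversibility, in a trial whose center holds the IND and is responsible for all safety monitoring (Section 16.0).

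**Working it through.** This is a comparison of time windows. The only published figure to reproduce is the visit window itself.

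**Inputs**
- Visit target 30 days, tolerance 14 days (Section 10.0).
- SAE window 30 days from last treatment (Section 17.2).
- Follow-up interval 3 months, tolerance 1 month (Section 10.0).
- Anchor: not stated in the calendar. Sections 13.1 and 17.2 both count from the last treatment, so the last dose is assumed here.

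**Step 1: visit window.** Earliest 30 − 14 = day 16. Latest 30 + 14 = day 44.

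**Step 2: uncovered part of the SAE window.** For a visit on day v, the uncovered days are max(0, 30 − v).

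| Visit day | Uncovered days | Share of 30 |
|---|---|---|
| 16 | 30 − 16 = 14 | 14/30 = 47% |
| 29 | 30 − 29 = 1 | 1/30 = 3% |
| 30 to 44 | 0 | 0% |

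The 47% is the edge of the window, not an expected value. The documents give no distribution of visit dates.

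**Step 3: next scheduled contact.** 3 − 1 = 2 months to 3 + 1 = 4 months. At 30.44 days per month:
- counted from the last dose: 2 × 30.44 = day 61 to 4 × 30.44 = day 122;
- counted from a day-16 visit: 16 + 61 = day 77 to 16 + 122 = day 138.

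Both are shown because the starting point of the follow-up interval is not stated either. Neither the survival call nor the imaging carries an AE assessment.

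**Step 4: Section 13.1 against the calendar.** The calendar runs from day 16 to day 44. Section 13.1, for early discontinuers, runs from no stated earliest day to day 30. They differ at both ends: Section 13.1 alone would admit a visit before day 16, and the calendar admits days 31 to 44. The mismatch also has a practical side. Section 13.1 lists a treatment delay of more than 28 consecutive days as a reason for discontinuation. Such a patient is already at about day 29 from the last dose, with a day or two left to return by day 30.

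**Step 5: dependence on the anchor.** Take a patient removed under Section 11.1 after 14 missed days. If the clock starts at the last dose, a day-16 visit could follow removal by 16 − 14 = 2 days and be the final AE assessment. If it starts at the decision to stop, the earliest visit is 14 + 16 = day 30 after the last dose, and the SAE gap closes for that patient. The missing anchor therefore changes the answer.

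**Step 6: effect of the fix.** If the last AE contact cannot precede day 30, the uncovered part falls from at most 14 days to 0. That alone does not supply follow-up of ongoing toxicity.

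**The case against.** The strongest reply is that the SAE duty in Section 17.2 does not depend on the visit. It runs for the full 30 days, and beyond for possibly related events. This is a single-center trial recruiting from that center's own clinics, and deaths, hospitalizations and life-threatening events may well become known without a scheduled call. A symmetric window also has a rationale: an earlier visit can precede new therapy that would confuse attribution. All of this stands, and it limits the point to scheduled ascertainment. It does not remove the point, because reporting depends on learning of the event and no scheduled contact asks.

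Several stronger readings are tempting, but the documents do not support them:
- **Every treated patient has the gap.** The target is day 30, and visits on days 30 to 44 leave nothing uncovered.
- **Patients removed for toxicity leave with it unresolved by definition.** The Section 11.1 rule turns on missed days, not on the grade at removal. A patient who recovers on day 14 also meets it.
- **Events are lost preferentially in those who stopped for toxicity, so the table understates severity.** No figure supports this. Under footnote 4, patients who stop without progression have more scheduled contact than progressors, although not AE assessments.
- **Section 13.1 forbids days 31 to 44.** Its language is advisory and addresses early discontinuers. It is a mismatch, not a prohibition.
- **The 5-calendar-day IRB deadline would be missed.** That deadline applies only to SAEs needing submission under an institutional SOP that the documents do not reproduce.

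**Conclusion.** The point holds as a gap in the visit schedule. A fully compliant End of Treatment visit on days 16 to 29 leaves 1 to 14 days of the protocol's own 30-day SAE window without a scheduled AE contact. The next contact, about 2 to 4 months on, is not designated to ask about adverse events. Related AEs still ongoing at End of Treatment have no scheduled follow-up, whenever the visit falls. Separately, Sections 10.0 and 13.1 do not agree on when the visit occurs.

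The sizes assume that the 30 days run from the last dose. How many patients are affected cannot be derived from the documents, and no loss of events is shown. The consequence is for the completeness of a descriptive secondary safety analysis; the response endpoint and its decision rule are unaffected. The change is worth making because it is small and specific.

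**What to change.** 1. State in the calendar that the End of Treatment visit is counted from the last dose, and state where the 3-monthly follow-up interval starts.
2. Reconcile Sections 10.0, 13.1 and 17.2 so that the last AE/SAE contact cannot fall before day 30. Either make the window 30 +14 days, or keep the earlier visit and add a phone question on AEs and SAEs at day 30 for patients seen before then.
3. Mark adverse event assessment on the existing 3-monthly call, limited to related AEs ongoing at End of Treatment and late, possibly related SAEs.

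**Cost.** The changes are to the calendar and to wording in Sections 13.1 and 17.2, with no new clinic visit. Keeping the early visit costs one short extra call for each patient seen before day 30. Moving the window instead means that some visits fall later, when new therapy may have begun and attribution is harder. The follow-up call becomes slightly longer for patients with unresolved toxicity.
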